7.5.1.3.2 Standard of Care (SOC) Group

The SOC group does not receive TransAeris stimulation for the first 120 hours of mechanical ventilation. SOC group patients will not be stimulated unless they are still on mechanical ventilation at 120 hours, at which point they will have an EMG recording made on the case report form, page 6. If intact bilateral EMG is not observed a competing event will be recorded on the competing event case report form, page 10. Otherwise the patient will be identified as a Cross-over patient on the daily post-op case report form, page 5, and follow the process for the Tx group as identified in section 7.5.1.3.1, with the start of TransAeris stimulation.

Any device deficiencies or competing events, that would inhibit or preclude weaning, should be indicated on the daily post-op case report form and the associated detail case report form for device deficiencies, page 12, or competing events, page 10, should be completed for all patients, Tx, SOC or cross-over.

A final EMG recording will be performed prior to electrode removal in all patients. Recordings will be made for a period of at least one minute during quiet, resting breathing or quiet, mechanical ventilation support.

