Another secondary comparator is the diaphragm EMG activity of the cross-over control patients. It is anticipated that we will see a difference in the bilateral EMG activity from baseline (POD 0) to the point of cross-over at POD 5. It is anticipated that the median frequency, during resting breathing should increase between baseline and the progression of VIDD at POD 5, then reverse back to baseline with TransAeris stimulation. This would be indicative of the use of more glycolytic fibers that have faster conduction velocities with VIDD and then the return of the use of oxidative slow twitch fibers as VIDD is treated with TransAeris.

The intended Outcome of TransAeris for the PICO model is a reduction in time on MV. For this study it is, as stated above for the comparators, a possible reduction in proportion on MV at 48 hours, a potential treatment of VIDD in cross-over patients on MV at 120 hours. Additionally, a difference in EMG analysis between the cross-over patients with more than 120 hours of MV will be assessed as an outcome.

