7.5 Procedures

7.5.1 Description of Investigational Procedures

Table 2 lists the data to be collected at each study interval. Study activities are recorded on the case report forms by the clinical coordinator or other clinician designated by the principal investigator. The clinician completing the form signs in the entry designated for completion and the principal investigator reviews all forms and signs in the designated location to indicate review and confirmation of the data entered.

Table 2a: Schedule of Study Activities and Data Collection – Initial All Patients

Activity/Procedure/ Assessment	Screening and Enrollment	At Time of Cardiac Surgery	ICU
Informed Consent	X		
Inclusion/non-inclusion criteria	X		
Demographics, medical history	X		
TransLoc electrode insertion		X	
Concomitant Interventions		X	
Serious adverse events		X	
Adverse device effects		X	

Activity/Procedure/ Assessment	Screening and Enrollment	At Time of Cardiac Surgery	ICU
Device deficiencies		X	
Randomization		X	
Concomitant Interventions			X
Start / Stop date and time of MV use			X
EMG Baseline recording			X

Table 2b: Schedule of Study Activities and Data Collection – Treatment Patients

Activity/Procedure/ Assessment	ICU
Start / Stop date of TransAeris stimulation	X
Competing events	X
Serious adverse events	X
Adverse device effects	X
Device deficiencies	X

Table 2c: Schedule of Study Activities and Data Collection – Control Patients

Activity/Procedure/ Assessment	ICU First 120hrs	ICU At 120hrs	ICU After 120hrs
EMG VIDD Progression recording		X	
TransAeris Start & Settings		X	
TransAeris Start/Stop & Settings			X
Competing events	X	X	X
Serious adverse events	X	X	X
Adverse device effects	X	X	X
Device deficiencies	X	X	X

Table 2d: Schedule of Study Activities and Data Collection – Conclusion All Patients

Activity/Procedure/ Assessment	Discharge	30 Days Post Electrode Removal
Serious adverse events	X	X
Adverse device effects	X	
Device deficiencies	X	
EMG Wean/Discharge recording	X	
TransLoc electrode removal	X	
Follow-up questionnaire		X

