8.4.2 Primary Efficacy Endpoint

The primary efficacy endpoints are the mechanical ventilation time and proportion of patients successfully weaned at 48- and 120-hours post-op. These will each be evaluated separately for efficacy. A wean will be considered successful if the patient is not reintubated within 48 hours of extubation. The mechanical ventilation time will be the cumulative proportion of time on mechanical ventilation over the 48- or 120-hour period from the entry to the ICU (recorded as ICU Admit Time on the procedure information case report form). If an extubation is attempted but is not successful (i.e., less than 48 hours) then that time will not be considered off of mechanical ventilation. The proportion weaned will be derived from the cumulative incidence function (CIF) of a competing risk analysis.

Data will be analyzed for all patients and using a predictive enrichment threshold of patients on mechanical ventilation. The enrichment strategy is applied to identify patients that may more likely respond to TransAeris stimulation and decrease variability, as per FDA guidance.(14) As the TransAeris treatment is not intended to produce immediate results, but rather is intended to prevent or treat VIDD, patients that are on MV for short periods are expected to have improved spontaneously and thus increase the variability in the outcome measures if included in analysis. Similarly, patients, during the initial hours of mechanical ventilation with paralytic anesthesia still impacting contraction, are not expected to respond to the treatment and thus excluding patients that are weaned from mechanical ventilation during the initial 10 hours post-op will be considered as not part of the predictive enrichment analysis. The data will be considered non-proportional and will be assessed using non-parametric techniques.

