8.4.3 Secondary Endpoints

Secondary endpoints are defined as follows:

- All-cause mortality through 30 days
- Mechanical Ventilation time, as the cumulative time on mechanical ventilation from ICU entry and paralytic reversal to successful wean,
- Ventilator-free days, defined(15) as time free from mechanical ventilation during first 28 days, where:
$$\begin{aligned} VFD28 &= (28 - \text{Time on MV}) \text{ if Time on MV is less than 28 days;} \\ &= 0 \text{ if Time on MV} \geq 28 \text{ days} \\ &= 0 \text{ if death within 28 days} \end{aligned}$$
- Hospital length of stay (admission to discharge)
- ICU length of stay
- Change in median frequency and total power of the power density spectrum (PSD) analysis of inspirations at baseline, pre-stimulation, and post-stimulation in cross-over control patients

All endpoints will be summarized and reported descriptively to characterize outcomes. No *a priori* hypothesis testing is planned for this study.

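### In cross-over controls the EMG is recorded on the ventilator before stimulation and normally off it afterwards, so the before/after change mixes stimulation with removal of ventilator support

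*Combined protocol and SAP*

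**What the plan says.** Section 8.4.3 lists as a secondary endpoint the change in median frequency and total power of the EMG power spectrum for "inspirations at baseline, pre-stimulation, and post-stimulation in cross-over control patients". Section 4.2 predicts the pattern: "median frequency, during resting breathing should increase between baseline and the progression of VIDD at POD 5, then reverse back to baseline". It interprets the second half as "then the return of the use of oxidative slow twitch fibers as VIDD is treated with TransAeris".

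Three recordings supply these values.

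- **Baseline:** in the ICU, once paralytics have been reversed (section 7.5.1.3, Table 2a).
- **Pre-stimulation:** at 120 hours, in controls who are still ventilated (section 7.5.1.3.2, Table 2c).
- **Post-stimulation:** Table 2c schedules no EMG after 120 hours. What remains is the Table 2d row "EMG Wean/Discharge recording", which section 7.5.1.3.2 places before electrode removal in all patients. Section 7.5.1.5 sets removal before ICU discharge or at 30 days after implant, whichever is first, and permits it earlier after successful extubation.

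On the state of the patient during recording, section 7.5.1.3.2 says: "Recordings will be made for a period of at least one minute during quiet, resting breathing or quiet, mechanical ventilation support". Nothing requires the state to be the same across a patient's recordings, and nothing says whether stimulation is off while the EMG is taken.

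**The concern.** The prediction in section 4.2 is worded for resting breathing only, while the recording rule accepts resting breathing or ventilator support. For a cross-over patient who weans, the scheduled before-stimulation value comes from one state and the scheduled after-stimulation value normally comes from the other. Time point and recording condition then change together.

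This matters because sections 7.2.3 and 8.4.3 list no other direct measure of the diaphragm. The EMG change is therefore the only physiological evidence in the plan on whether stimulation treats established diaphragm dysfunction. Quantifying EMG is a stated secondary objective (section 6.2), and section 8.1 says the data will inform the pivotal trial. If the plan is followed as written, a change from on-ventilator to off-ventilator recording will be credited to stimulation. Once the electrodes are out, a matched recording cannot be recovered.

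**Working it through.** **1. How many patients carry the endpoint.** Section 4.2 expects 2 to 3 of 15 controls to be on MV at 5 days. Inputs from the same section: 15 controls, positive predictive value 56.5%, 35% of prolonged-ventilation patients still on MV at 5 days.

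Expected cross-overs = 15 × 0.565 × 0.35 = 2.97, at the top of the plan's range, so the figure is reproduced. With p = 0.565 × 0.35 = 0.19775 and n = 15, the exact binomial gives P(0) = 3.7%, P(at most 1) = 17.2% and P(5 or more) = 15.9%. These counts are before any loss to death, absent bilateral EMG or failure to wean.

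**2. The state at each recording, for a cross-over patient who weans.**

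| Recording | When | Ventilator state | Basis |
|---|---|---|---|
| Baseline | ICU, after paralytic reversal | On MV | Inferred: in the ICU on day 0, and still on MV at 120 hours |
| Pre-stimulation | 120 hours | On MV | By definition of cross-over |
| Post-stimulation | Before electrode removal | Normally off MV | Inferred from the wean/discharge label and the removal rule |

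The first step, baseline to 120 hours, is matched on ventilator status. The second step, 120 hours to final, normally is not.

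**3. What the second step measures.** Write S for the change in median frequency that goes with the period of stimulation, and V for the change caused by removing ventilator support. The planned comparison yields one number per patient:

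final − pre-stimulation = S + V.

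No planned analysis estimates V, so S cannot be recovered. A cross-over patient never weaned by day 30 would be recorded on MV and would have V = 0. The like-for-like pairs that the schedule itself produces therefore come mainly from patients who did not wean.

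**4. Whether numbers could rescue it.** If three readings are exchangeable noise, the middle one is the highest with probability 1/3. All of 2 patients would then show a rise and return with probability (1/3)² = 11%, and all of 3 with (1/3)³ = 3.7%. The smallest two-sided sign-test p-value, 2 × 0.5ⁿ, is 0.50 for 2 patients and 0.25 for 3. A V shared by all patients would not average out with more of them.

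**5. Data already collected that bear on V.** Baseline and final EMGs are taken in all patients. Controls weaned before 120 hours normally go from on-MV to off-MV with no stimulation at all. By the plan's own projection, 12 to 13 of the 15 controls (15 − 3 to 15 − 2) are not on MV at 120 hours, before deaths are removed. Section 8.4.3 limits the EMG analysis to cross-over patients and leaves these recordings unused.

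**The case against.** The strongest reply is that this is a secondary, descriptive endpoint in a handful of patients, with no hypothesis test, and that the stated objective is only to assess whether EMG can be quantified. Mixed recording conditions do not prevent that. This stands, and it limits how much weight the point deserves. It does not remove the point, because section 4.2 already attaches a causal reading to the pattern.

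The documents do not support several stronger readings that a reader might infer.

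- **That ventilator status cannot be sorted out afterwards.** Case report form page 5 records ventilatory support daily (section 7.5.1.3), and Table 2a collects MV start and stop times. If EMGs are timed, on or off MV can be linked to each. That would show a mismatch, but it would not supply a matched pair. No ventilator mode, support level or sedation field is described. Page 6 itself is not reproduced, so its fields cannot be judged.
- **That all three recordings differ in condition.** Baseline and 120 hours are both on MV in these patients.
- **That the baseline is contaminated by paralytics.** Section 8.4.2 does speak of patients "during the initial hours of mechanical ventilation with paralytic anesthesia still impacting contraction", but it does so to justify the 10-hour enrichment rule. Section 7.5.1.3 requires paralytic reversal before the baseline EMG. Residual sedation is possible but not shown.
- **That no cross-over patient can have a matched pair.** The plan does not say that the final recording must follow extubation.
- **That the predicted rise and return would appear without diaphragm dysfunction.** To imitate the return, removing support would have to lower median frequency. The documents do not show that it does.

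**Conclusion.** The point holds for the second step only. In cross-over controls who wean, the change from before to after stimulation is normally confounded with coming off the ventilator, and the planned analysis cannot separate the two. It affects every cross-over patient whose final EMG is taken after extubation, out of an expected 2 to 3. The size and direction of the effect cannot be derived from the documents: it could imitate a return to baseline or hide one.

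The conclusion rests on two inferences: that cross-over patients are on MV at baseline, and that a wean/discharge recording in a weaned patient is usually made off MV. Primary safety and efficacy results are unaffected. The change is worth making because it is cheap, and not because the trial fails without it.

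**What to change.** 1. In section 7.5.1.3.2, Table 2c and section 8.4.3, add for cross-over patients a one-minute EMG taken while still on MV before extubation, where feasible, with the stimulator paused for the recording. Name it as the primary post-stimulation value.
2. With every EMG, record the time, ventilatory support, sedation and stimulator status, and link the entry to the support record on case report form page 5.
3. Report the change in median frequency and total power for pairs in the same ventilatory state. Keep the off-ventilator final recording, but show it separately and label it as such.
4. Report the baseline-to-final EMG change in controls weaned before 120 hours as an unstimulated reference for the effect of recording condition. It is imperfect, because these patients weaned earlier and their baseline-to-final interval also spans early recovery from surgery, but it needs no new data.

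The cost is a few form fields and one short extra recording in an expected 2 to 3 patients, using leads and a recorder already in place. The downside is that extubation cannot always be foreseen, so some of these recordings will be missed and there may be fewer matched pairs. Matching removes the ventilator difference only. With no unstimulated patients planned after 120 hours, the passage of time would still be mixed with stimulation, and the wording of the conclusion should say so.

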7.5.1.4 Competing Events

At any point during the study both groups will be monitored for competing events that preclude or impede the progression of weaning, i.e. causes other than VIDD that are the source of an inability to wean. These are typically adverse events, unrelated to the device or procedure that will also be recorded in detail, as per Section 15. Identification as a competing event, with time and date of the event, will establish the point of censoring for purposes of analysis of efficacy outcomes. An indication of the occurrence is recorded on the daily post-op case report form (page 5) with more detail of the event, including specific cause of the event and status of the event (as described below) recorded on the competing event detail case report form (page 10). The patient may continue with the TransAeris therapy, if initiated, at the discretion of the clinician.

The event of interest is successful wean from mechanical ventilation and is classified as a Status=0 event. Death prior to successful weaning from mechanical ventilation is a competing event that precludes further weaning and would be classified as a Status=2, right censored event. Other events that hinder the event of interest and alter the probability of occurrence are classified as a Status=1, right censored event. This is depicted below in Figure 3: Competing Event Model.

[figure not shown]

Figure 3: Competing Event Model

The pre-specified competing events and censoring status are provided in Table 3, below. The events that would hinder weaning from mechanical ventilation are right censored with Status 1. Since an intact phrenic lower motor neuron is required for the stimulation to propagate through the diaphragm muscle, bilateral phrenic function, as identified by an observed EMG on both left and right hemidiaphragms, is necessary for the TransAeris stimulation to be effective. Lack of observed bilateral function, indicating a damaged phrenic nerve prior to or during surgery, is considered a competing event that would impede weaning with TransAeris. Additional right censor events may be considered that would meet the definition of precluding or impeding the event of interest (i.e. successful wean) from occurring.

Table 3: Competing Events

Event type	Censor Status	Description	Observed (Suarez-Pierre)
Desired Event	0	Successful wean	39.7%*
Right Censor	2	Death prior to wean, precludes event of interest	20%**
Right Censor	1	Renal failure w/ dialysis initiated post-operatively	9.7%
Right Censor	1	Hemorrhage requiring reoperation	10.4%
Right Censor	1	Delayed Sternal Closure, reoperation	8.3%
Right Censor	1	Sepsis	6.1%
Right Censor	1	TIA or CVA	5.8%
Right Censor	1	Cardiogenic shock, cardiac arrest	13.8%
Right Censor	1	Lack of bilateral diaphragm EMG function	n/a

*Percentage no longer on MV at 48 hours, from Suarez-Pierre (2019) Figure 1

**Approximate 96 hour predicted mortality from Suarez-Pierre (2019) Figure 2

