7.5.1.3 Electrode Placement and Device Use

All subjects will be randomized to treatment or control groups prior to implantation of the TransLoc electrodes. Subjects not implanted will be withdrawn from the study. The procedure information is recorded on the case report form, page 4. Specific information concerning the cardiac procedure that the patient is undergoing is recorded on the form as well as procedure time, pump time and any concomitant interventions that the patient undergoes at the time of the cardiac surgery. The device tracking information for the electrodes are recorded in the procedure information as well as an indication of successful electrode placement, or occurrence of an adverse event, competing event or device deficiency.

Patients are randomized to the Treatment or Standard of Care groups as per section 7.4.2.1. The group assignment is recorded on the Post-Op case report form, page 5. This case report form is completed for each patient for each day in protocol, beginning with the day of surgery as day 0. The reversal or time when paralytics are worn off is recorded as well as the current ventilatory support in terms of intubation, extubation, and any type of post-extubation ventilatory support that may be required.

Once the paralytics have been reversed from the surgery, an initial diaphragm EMG is recorded on case report form, page 6. If bilateral EMG is not observed, then a competing event is recorded as described below in section 7.5.1.4.

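### Non-fatal Status 1 events stop efficacy analysis time with their role in the CIF unstated, so the primary proportion weaned tends to be too high if they are censored and too low if they compete

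*Combined protocol and SAP*

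**What the plan says.** Section 8.4.2 names mechanical ventilation (MV) time and the proportion successfully weaned at 48 and 120 hours as the primary efficacy endpoints. Success requires only that the patient is not reintubated within 48 hours of extubation; a complication does not disqualify a wean. The proportion is to come from the CIF of a competing risk analysis.

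Section 7.5.1.4 controls what enters that analysis:

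- Identification of a competing event, with its time, "will establish the point of censoring for purposes of analysis of efficacy outcomes".
- Death before weaning "is a competing event that precludes further weaning and would be classified as a Status=2, right censored event".
- For the non-fatal complications the protocol gives this rule: "Other events that hinder the event of interest and alter the probability of occurrence are classified as a Status=1, right censored event".
- Table 3 lists seven Status 1 items: six complications (for example "Renal failure w/ dialysis initiated post-operatively") and absent bilateral diaphragm EMG. Section 7.5.1.3 has the EMG item recorded at the initial recording after paralytic reversal: "If bilateral EMG is not observed, then a competing event is recorded as described below in section 7.5.1.4".
- The list is open: "Additional right censor events may be considered that would meet the definition of precluding or impeding the event of interest".
- The stated purpose is to separate out "causes other than VIDD that are the source of an inability to wean".

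Stimulation may continue after a Status 1 event at the clinician's discretion. Daily forms (7.5.1.3) and MV start and stop times (Table 2a) are still collected.

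**The concern.** Death and the Status 1 events carry the same right-censor label under a heading about competing events, so the label does not show how Status 1 enters the CIF. Two codings are possible, and in general neither returns the proportion that 8.4.2 names.

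- **Status 1 censored.** The estimator assumes that a censored patient would go on to wean like the event-free patients still ventilated. Section 7.5.1.4 says these events hinder weaning and change its probability. The censoring is therefore informative and the estimate too high.
- **Status 1 competing.** The CIF validly estimates weaning without a prior listed event. A patient who has a listed event and then weans by the time point counts as not weaned, so the estimate is too low for the named endpoint.

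The trial is descriptive, so its estimates are its product. Section 7.3 sets outcomes against literature, and section 8.1 carries them into the pivotal trial's design parameters. The literature rates in Table 1 (section 4.2) count patients on MV at fixed times, with no stated stop at complications, so the comparison would not be like with like. The list can also be extended in an open-label trial, which lets labelling itself move the result.

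**Working it through.** **Plan figures used (section 4.2, Table 1).** On MV at 48 h: 73,391/111,307 = 65.9%. On MV at 120 h: 38,614/(1,698 + 109,380) = 34.8%, leaving out the dataset that does not report 120 h. Both reproduce.

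**Count example.** 15 patients, no deaths. Six wean before 24 h. Of the nine still ventilated, four have a Status 1 event at 24-30 h, and one of these weans at 44 h. Two of the other five wean at 40 h.

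- Named endpoint at 48 h: (6 + 1 + 2)/15 = 60.0%
- Status 1 censored: 6/15 + (9/15)(2/5) = 64.0%
- Status 1 competing: (6 + 2)/15 = 53.3%

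**Model for control patients with prolonged MV (PMV, at least 24 h).**

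Assumptions not in the documents:

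- a share p = 30% would have a Status 1 event, timed uniformly over 0-48 h
- the wean hazard is multiplied by r = 0.25 or 0.5 after the event
- 5% are dead by 48 h and 10% by 120 h
- hazards are constant within 24-48 h and within 48-120 h

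For scale, the six quantified Status 1 rates in Table 3 run from 13.8% (the largest alone, full overlap) to 9.7 + 10.4 + 8.3 + 6.1 + 5.8 + 13.8 = 54.1% (no overlap). Table 3 gives neither overlap nor timing.

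True weaned: 100 - 65.9 - 5 = 29.1% at 48 h; 100 - 34.8 - 10 = 55.2% at 120 h.

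With event-free wean hazard λ and death hazard δ per hour, calibrated to those figures:

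- Censored, 48 h: A = λ/(λ+δ) × [1 - exp(-24(λ+δ))]
- Competing, 48 h: B = ∫ from 24 to 48 of λ(1 - 0.30u/48) exp(-(λ+δ)(u-24)) du
- From 48 to 120 h, increment I = exp(-24(λ+δ)) × λ₂/(λ₂+δ₂) × [1 - exp(-72(λ₂+δ₂))]. A grows by I, and B by 0.70 × I, because no new events occur after 48 h.

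For r = 0.25: λ = 0.01825, δ = 0.00256, λ₂ = 0.01092, δ₂ = 0.00144. A(48) = 0.877 × 0.393 = 0.345; B(48) = 0.269; I = 0.607 × 0.884 × 0.589 = 0.316. So A(120) = 0.661 and B(120) = 0.2693 + 0.70 × 0.316 = 0.4905.

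For r = 0.5: λ = 0.01685, δ = 0.00256, λ₂ = 0.00913, δ₂ = 0.00143, by the same steps.

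| | True | Censored, r = 0.25 / 0.5 | Competing, r = 0.25 / 0.5 |
|---|---|---|---|
| 48 h | 29.1% | 34.5% / 32.3% | 26.9% / 25.2% |
| 120 h | 55.2% | 66.1% / 61.2% | 49.1% / 45.5% |

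Table 3 cites about 20% predicted mortality at 96 h. With 20% dead by 120 h (λ₂, δ₂ = 0.00652, 0.00429 for r = 0.25; 0.00558, 0.00428 for r = 0.5), the 120 h figures are true 45.2%, censored 54.3% / 50.4%, competing 40.8% / 37.9%. The pattern is the same.

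**Sampling error.** About 15 × 0.565 = 8.5 PMV patients are expected per arm. One-arm standard error: √(0.291 × 0.709/8.475) = 15.6 points at 48 h; √(0.552 × 0.448/8.475) = 17.1 points at 120 h.

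**Effect of labelling alone.** Suppose 7 of 15 wean in each arm (46.7%), and Status 1 is labelled at the start on two never-weaned patients in one arm and four in the other. With censoring the arms read 7/13 = 53.8% and 7/11 = 63.6%.

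**The case against.** The best defence is that the competing reading is meant. Section 8.4.2 specifies a competing risk analysis, where death has to be a competing cause. Since death carries the same right-censor label, the label cannot mean ordinary censoring, and Status 1 may be competing too. The competing-event figure in 7.5.1.4, not available in the text reviewed, may settle it. That would remove the upward bias. It would not restore the named endpoint, because the status definitions say death precludes weaning while Status 1 events hinder it, so some Status 1 patients can wean.

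Isolating failure to wean from VIDD is also a legitimate aim. It supports a labelled secondary estimate, but 8.4.2 does not name that quantity as primary.

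Several stronger conclusions might be inferred and are not supported:

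- *That neither coding can ever be right.* Censoring is right if the events leave weaning unchanged, and competing coding is exact if no Status 1 patient weans by the time point. With r = 0.1 and otherwise the same assumptions, competing gives 28.2% against 29.1% at 48 h and 52.2% against 55.2% at 120 h.
- *That follow-up is lost.* Only analysis time stops; the data to compute the named proportion are still collected.
- *That the full analysis set in 8.3 is breached.* It defines who is analysed, and these patients remain in it under either coding.
- *That absent EMG dominates.* The protocol describes "Lack of observed bilateral function, indicating a damaged phrenic nerve prior to or during surgery", but Table 3 gives no rate and known or pre-existing phrenic paralysis is a non-inclusion criterion. Only undetected or surgical cases remain.
- *That the pivotal size of about 192 is wrong.* It rests on literature proportions on MV at 48 h (65.9% vs 45.9%), which Status 1 coding does not define.
- *That the arms are necessarily compared unfairly.* With no treatment effect and equal event rates, the expected difference does not move. The unequal labelling example shows a possibility, not a prediction.

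**Conclusion.** The concern holds in this form. The readable plan stops efficacy analysis time at non-fatal events without stating their role in the CIF, and outside the limiting cases each coding moves the primary proportion weaned away from its definition in 8.4.2. The upward direction under censoring follows from the protocol's own statement that the events hinder weaning.

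The size depends on assumptions about event frequency, timing, later weaning and mortality. In the illustration, censoring adds 3.2 to 5.4 points at 48 h and 6.0 to 10.9 at 120 h; competing coding removes 2.2 to 3.9 and 6.1 to 9.7. These figures are for PMV patients. Among all implanted patients the shift is diluted, since the plan expects 43.5% to wean before 24 h.

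All these shifts are smaller than the one-arm standard error of 16 to 17 points, and no hypothesis test is planned, so this is not a question of false-positive risk. It is an avoidable bias or ambiguity in a primary estimate that will be set beside literature and passed to the pivotal design. It should be fixed.

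**What to change.** In 7.5.1.4, Table 3 and 8.4.2:

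- Define the primary proportion weaned as the CIF with successful wean as the event and death before wean as the only competing event. Drop the right-censor label for death.
- Censor only patients still alive and ventilated at the end of the window, or withdrawn. With complete follow-up the estimate is then simply the share of analysed patients weaned by 48 and 120 h.
- Record Status 1 events, including absent bilateral EMG, without ending analysis time for weaning.
- Report the stop-at-Status-1 analysis as a VIDD-specific sensitivity analysis, labelled as such, stating whether Status 1 is censored or competing.
- Freeze the Status 1 list before the first randomisation.

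The cost is protocol wording and status recoding; no new data are needed. The downside is that weaning failures from causes other than VIDD stay in the primary estimate and add some noise.

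### Section 7.5.1.4 and Table 3 right-censor death before weaning, which is incompatible with the cumulative incidence function that section 8.4.2 prescribes for the primary proportion weaned

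*Combined protocol and SAP*

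**What the plan says.** Section 8.4.2 (Primary Efficacy Endpoint) names the estimator: "The proportion weaned will be derived from the cumulative incidence function (CIF) of a competing risk analysis". It does not name the CIF estimator or say how the status codes enter it.

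Section 7.5.1.4 (Competing Events) sets the status rules:

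- Weaning: "The event of interest is successful wean from mechanical ventilation and is classified as a Status=0 event".
- Death before weaning "is a competing event that precludes further weaning" and, in the same sentence, "would be classified as a Status=2, right censored event".
- Complications: "Other events that hinder the event of interest and alter the probability of occurrence are classified as a Status=1, right censored event".
- For any competing event, the recorded date and time "will establish the point of censoring for purposes of analysis of efficacy outcomes".

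Table 3 follows the same scheme. It lists death before weaning as a right-censoring event with status 2, seven complications as right-censoring events with status 1, and the wean with status 0.

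**The concern.** Right-censoring a death tells the estimator that the patient left observation but could still have weaned later at the same rate as those who remain. A dead patient cannot wean. A CIF instead keeps the death in the calculation as an outcome that rules out weaning. An analyst who follows 7.5.1.4 and one who follows 8.4.2 would therefore report different values of a primary endpoint from the same data.

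The difference is not neutral between arms, because the upward shift from censoring depends on how many patients die before weaning and when. Section 8.1 says the data will inform the design and statistical parameters of the pivotal trial. Section 4.2 plans that trial around a 20-point difference at 48 hours. An estimate that moves by several points with mortality is a poor input to that plan.

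**Working it through.** **The plan's own figures.** The documents state no value for the proportion weaned in this trial under either estimator. The nearest formal figure is the pivotal size in section 4.2, about 192 patients for 65.9% v 45.9% still ventilated at 48 hours. With two-sided alpha 0.05 and 80% power (power is not stated; 80% is assumed):

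n per arm = [1.96·√(2 × 0.559 × 0.441) + 0.842·√(0.659 × 0.341 + 0.459 × 0.541)]² / 0.20² ≈ 95.6, so 96 per arm and 192 in total. Then 192 / 0.565 = 339.8, so 340 implanted. Both figures reproduce. They serve only as a yardstick for the bias.

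**Inputs for the bias**

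- Weaned at 48 h: 39.7% (Table 3; equal to 1 − 60.3% in Table 1). The footnote describes it as "Percentage no longer on MV at 48 hours", so it may include deaths.
- Off ventilation at 120 h: 1 − 29.1% = 70.9% (Table 1, same cited dataset), here taken to include deaths.
- Deaths before weaning: Table 3 gives 20%, footnoted "Approximate 96 hour predicted mortality from" a cited study. Deaths by 48 or 120 h are not given, so I assume 5%, 10% and 20%.
- These are rates in patients with at least 24 h of ventilation.

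**Formula.** Let w be the true proportion weaned and d the proportion dead before weaning, with constant cause-specific hazards. The total cumulative hazard is H = −ln(1 − w − d). The weaning part is H·w/(w + d). Censoring death gives 1 − KM = 1 − exp[−H·w/(w + d)]; the CIF is w.

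Example at 48 h with d = 20%: H = −ln(0.403) = 0.909; weaning part = 0.909 × 0.397/0.597 = 0.604; 1 − KM = 1 − exp(−0.604) = 45.4%, against 39.7%.

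| Time | Deaths d | CIF (w) | 1 − KM | Excess (points) |
|---|---|---|---|---|
| 48 h | 5% | 39.7% | 40.9% | +1.2 |
| 48 h | 10% | 39.7% | 42.2% | +2.5 |
| 48 h | 20% | 39.7% | 45.4% | +5.7 |
| 120 h | 5% | 65.9% | 68.3% | +2.4 |
| 120 h | 10% | 60.9% | 65.4% | +4.5 |
| 120 h | 20% | 50.9% | 58.8% | +7.9 |

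If the 39.7% at 48 h does include the deaths, w falls to 34.7%, 29.7% and 19.7%, and the same formula gives an excess of +1.0, +1.8 and +2.5 points.

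**All patients.** Suppose the patients who do not need 24 h of ventilation all wean alive. The excess is then multiplied by the positive predictive value 13/23 = 0.565 (section 4.2): 5.7 becomes 3.2 points at 48 h, and 7.9 becomes 4.5 points at 120 h.

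**Between arms**

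- Equal wean hazards (cumulative 0.598) with death hazards of 0.1 and 0.4: 1 − KM is 45.0% in both arms. The CIF is 43.0% in the arm with 7.2% deaths and 37.8% in the arm with 25.3% deaths. Censoring death hides a 5.2-point deficit.
- Unequal wean hazards: both arms truly wean 45.2% (= 100 − 20 − 34.8, the last being the pooled 120 h figure in Table 1), with deaths of 10% v 20%. 1 − KM is 48.2% v 51.9%, so the arm with twice the deaths looks 3.7 points better. A small true shortfall in that arm would come out reversed.

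**Trial-sized example.** Take 15 patients, 6 weaned and no other censoring. With 2 deaths before the weans, 1 − KM = 6/13 = 46.2% and the CIF = 6/15 = 40.0%. If the deaths follow the last wean, both are 40.0%.

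**Status 1 events.** A CIF does not repair the censoring of complications. Take 15 patients in the order death, two Status 1 censorings, two weans, death, one Status 1 censoring, four weans. The Aalen-Johansen CIF is 2 × (14/15)/12 + 4 × 0.70/8 = 0.156 + 0.350 = 50.6%, against a crude 6/15 = 40.0%.

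**The case against.** The strongest reply is that 8.4.2 defines the endpoint and names a CIF, and that 7.5.1.4 calls death a competing event and gives it a code apart from the complications, which simple censoring would not need. This stands against the stronger reading that the plan specifies 1 − KM. It does not: it gives two incompatible instructions, and the more operational one, with its date rule and code table, is wrong for the named estimator.

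A reader might also infer that excess deaths would generally show up as a weaning benefit. The documents do not support that. The 3.7-point example builds in a higher wean hazard in the high-death arm (cumulative 0.732 v 0.657); with equal wean hazards, censoring hides a deficit and creates no benefit. Nor would excess deaths go unseen: 30-day mortality is a separate endpoint, ventilator-free days score death as zero, and section 7.5.1.7 compares adverse events between arms.

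Code 0 for the wean might be read as a cause of the bias. It is not. Under a column for censor status, 0 can mean not censored. It is a programming hazard only, because many routines take 0 as censored. The competing event model figure was not available to me, so I do not claim that a code for patients still ventilated is missing.

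Finally, the study is descriptive, has up to 30 implants and tests no prior hypothesis. That limits the consequence but does not make the two sections agree.

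**Conclusion.** The contradiction is real and affects a primary efficacy endpoint. If death is censored as 7.5.1.4 says, the proportion weaned is overstated by about 1 to 6 points at 48 hours and 2 to 8 points at 120 hours among patients with at least 24 hours of ventilation, and by roughly 0.565 of that among all patients.

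These sizes rest on an assumed 5% to 20% of deaths before weaning, constant cause-specific hazards, and a 96-hour predicted mortality used as the upper value at both time points. The bias is zero if all deaths come after the last wean. The effect falls on the primary estimates and on the pivotal planning that they inform; no formal error rate is involved.

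**What to change.** 1. In 7.5.1.4 and Table 3, delete the right-censoring label for death, and exempt death from the sentence that makes a competing event the point of censoring.
2. In 7.5.1.4 and 8.4.2, state that death before successful wean enters an Aalen-Johansen CIF as a competing event and is never censored.
3. Define distinct codes for successful wean, death before wean, Status 1 complication, and still ventilated at the end of the window or follow-up stopped. Declare the event code explicitly in the analysis.
4. State how Status 1 events enter the estimate. Say that the CIF equals the simple proportion weaned only if nobody, including patients with a Status 1 event, is censored before the time point.

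The cost is a few sentences, a recoded table and matching status codes on the competing event form. No new data are needed, because the type, date and time of each event are already to be recorded.
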